7.1 STATISTICAL DESIGN - MODEL

For the purposes of the exploratory analysis, the primary PK endpoints for BI 695501 will be estimated using an analysis of variance (ANOVA) model on the logarithmic scale with fixed effects for treatment, and baseline body weight (continuous).

The ANOVA model is described by the following equation:

$$y_{ij} = \mu + \tau_i + \beta * \text{weight}_{ij} + e_{ij}, \text{ where}$$

y_{ij} = logarithm of PK parameter measured on subject j receiving treatment i,

μ = the overall mean,

τ_i = the i-th treatment effect, $i = 1, 2$ (1=Test, 2=Reference),

β = the slope parameter for the baseline body weight covariate,

weight_{ij} = baseline body weight of subject j receiving treatment i,

e_{ij} = the random error associated with the j-th subject, receiving treatment i,

where $e_{ij} \sim N(0, \sigma_i^2)$ are independent random variables.

The randomisation will be stratified by site, but this is considered to be a logistical stratification and will therefore be not included in the primary model.

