7.2 NULL AND ALTERNATIVE HYPOTHESES

The relative bioavailability of BI 695501 using autoinjector (A) compared to BI 695501 using prefilled syringe (B) will be estimated, in an exploratory manner, by the ratios of the geometric means (A/B) for the primary endpoints using the ANOVA described in [Section 7.1](#). All PK further parameters of interest will be analysed descriptively.

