7.3.1 Primary endpoint analyses

In an exploratory manner, the relative bioavailability of BI 695501 using autoinjector (A) compared to BI 695501 using prefilled syringe (B) will be estimated by the ratios of the geometric means (A/B) for the primary PK endpoints. Point estimates of relative bioavailability, the ratios (A/B) of the geometric means for the primary PK endpoints (see [Section 5.1.1](#)), and their two-sided 90% CIs will be provided for the overall comparison A versus B.

The PK endpoints will be log-transformed (natural logarithm) prior to fitting the ANOVA model (see [Section 7.1](#)). For each PK endpoint, the difference between the means for $\log(A)$ - $\log(B)$ will be estimated by the difference in the corresponding adjusted means (least-squares means), and a two-sided 90% CI based on the t-distribution will be computed. These quantities will then be back-transformed to the original scale to provide the point estimate and 90% CIs for the corresponding ratio of geometric means (A/B) for each PK endpoint.

The ANOVA will be conducted on the PK Analysis Set (PKS). The PKS will consist of all randomized subjects who receive the single dose of trial medication (BI 695501 using autoinjector or BI 695501 using prefilled syringe), and have at least one evaluable primary PK parameter, and are without important protocol deviations or violations thought to significantly affect the PK of BI 695501.

Pharmacokinetic parameters of a subject will be included in the analysis unless the subject has an important protocol violation relevant for the evaluation. Whether a protocol violation is important will be decided no later than in the Report Planning Meeting.

Reasons for exclusion of single pharmacokinetic parameters can for example be:

- Time deviations
- Use of restricted medications
- Dosing errors

It will also be decided in the Report Planning Meeting which subjects are to be included in the PKS.

Details of the presentation and analysis of PK data will be provided in the Trial Statistical Analysis Plan (TSAP).

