7.6 RANDOMISATION

Subjects will be randomized to one of the two treatments in a 1:1 ratio. The block size will be documented in the CTR.

The sponsor will arrange for the randomization as well as packaging and labelling of trial medication. The randomization list will be generated using a validated system, which involves a pseudo-random number generator and a supplied seed number so that the resulting allocation is both reproducible and non-predictable. Randomization will be stratified by:

- site (2 levels and for logistical reasons only)
- baseline body weight category with ranges:
 - low: ≤ 60.0 kg
 - medium: > 60.0 to ≤ 90.0 kg
 - high: ≥ 90.0 kg

and will be randomized sequentially (the lowest sequentially available randomization number).

The randomization list will contain additional blocks to allow for subject replacement (refer to [Section 3.3.5](#)).

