Proprietary confidential information © 2016 Boehringer Ingelheim International GmbH or one or more of its affiliated companies

Table 7.7: 2 Power (%) for concluding bioequivalence (acceptance range 80-125%) based on a geometric coefficient of variation around 50% and for different expected ratios of geometric means (test/reference) in a parallel trial (N=160).

gCV [%]	Ratio [%] [*]			
	100	104	108	112
32	>99%	98%	90%	71%
45	89%	83%	68%	55%
50	81%	75%	61%	-
54	74%	68%	55%	-

^{*}Ratio of geometric means (test/reference) for a PK endpoint is defined by $\exp(\mu_T)/\exp(\mu_R)$.

The calculations were performed using nQuery Version 2.0.1.0.

Therefore, with the expectation that there is less variability in this planned trial, there should be more than 70% power to have the resulting 90% confidence interval of the ratio of the gMeans lying within the range of 80-125%. The reason for less expected variability is that the drug is now to be administered in the thigh, and there is also expected to be slightly less variability when adjusting for baseline body weight.

Thus a total sample size of up to 160 subjects is planned for this trial and with no planned adjustment for drop-outs.

Boehringer Ingelheim
BI Trial No.: 1297.13
c11534380-01

23 Aug 2016

Trial Protocol

Page 51 of 58

Proprietary confidential information © 2016 Boehringer Ingelheim International GmbH or one or more of its affiliated companies

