3. TRIAL DESIGN

3.1. GENERAL DESCRIPTION

Trial 1297.13 is a 14-week, randomized, single-dose, open-label trial in healthy volunteers.

Each subject will receive one subcutaneous injection with either 40 mg BI 695501 autoinjector (AI) or 40 mg BI 695501 prefilled syringe (PFS) followed by an observation period of approximately 57 days and an additional safety follow-up period up to 70 days after the trial drug administration. Subjects who meet all the inclusion criteria and none of the exclusion criteria will be randomly assigned to one of the two groups with a 1:1 allocation ratio. Randomization will be stratified by site (2 levels and for logistical reasons only) and body weight category (low: ≤ 60.0 kg, medium: > 60.0 to < 90.0 kg, high: ≥ 90.0 kg).

It is planned to include 160 healthy male and female subjects (at least 30% of each gender will be included in the trial) with a broad range of weight for the primary analysis report describing the PK profiles of BI 695501 given in a PFS and an AI as well as the assessments of safety and immunogenicity. All efforts will be made to enroll subjects in all subgroups, in order to ensure a wide distribution of weight in the study.

This trial will have a screening period of up to 28 days. The subject will check in to the trial center on Day-1, will be randomized and dosed on Day 1, and will be resident until the Day 8 discharge procedures are complete. All subjects will remain in the clinic until Day 8 after dosing. The subject will then return to the clinic for 7 ambulatory visits on Days 10, 15, 22, 29, 36, 43 and 57 (End-of-Trial [EOT] visit).

Additionally, all adverse events (AEs), regardless of relatedness, will be collected until up to 10 weeks after the administration of trial medication. Adverse events not fully resolved at the safety follow-up (SFU) visit (Day 70 visit) will be followed until recovery or in case of persistency, sufficient characterization has been achieved and the investigator and medical monitor agree to not pursue them further.

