7. STATISTICAL CONSIDERATIONS

7.1. ADJUSTMENTS FOR COVARIATES AND FACTORS TO BE INCLUDED IN ANALYSES

The following covariates and factors are used in the analyses. For details of their inclusion in the models, see the specific analysis section.

- Treatment group (BI 695501 using AI or BI 695501 using PFS)
- Baseline body weight (continuous variable)

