7.4. EXAMINATION OF SUBGROUPS

7.4.1. RANDOMIZATION STRATIFICATION FACTORS

Disposition will be displayed for each randomization strata:

- Baseline body weight (≤ 60.0 kg, $> 60.0 - < 90.0$ kg, ≥ 90.0 kg),
- Site

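### Randomisation is stratified by site but site is left out of the model for the geometric mean ratios, so the 90% CIs are wider than needed if exposure differs between sites

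*Protocol*

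**What the plan says.** Protocol section 7.6 stratifies the 1:1 randomisation by weight category and by "site (2 levels and for logistical reasons only"). SAP section 3.1 repeats it: "Randomization will be stratified by site (2 levels and for logistical reasons only) and body weight category".

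Protocol section 7.1 models the log PK parameter on treatment and continuous baseline weight, and excludes site from that model explicitly: "The randomisation will be stratified by site, but this is considered to be a logistical stratification and will therefore be not included". SAP section 7.1 lists the same two terms, treatment group and "Baseline body weight (continuous variable"). As a stratification factor, site appears in the SAP only in section 7.4.1: "Disposition will be displayed for each randomization strata".

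From this model come the geometric mean ratios, and "their two-sided 90% CIs will be provided for the overall comparison A versus B" (protocol section 7.3.1). Section 7.2 sets their status: the relative bioavailability "will be estimated, in an exploratory manner, by the ratios of the geometric means (A/B"). Section 7.7 nevertheless supports N=160 with a power statement: "there should be more than 70% power to have the resulting 90% confidence interval" of the ratio inside 80-125%.

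**The concern.** Why site was made a stratum, logistics or otherwise, has no bearing on the variance. With allocation balanced within site, a difference in exposure between the sites falls about equally on both arms and largely cancels from the contrast. A model without site still counts that difference as residual error. The standard error is then larger than the true sampling error of the contrast, and the nominal 90% interval covers more than 90% of the time.

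The two strata are also treated differently. Weight is adjusted for, and section 7.7 expects that adjustment to reduce variability slightly. The same argument applies to site.

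What is at stake is precision only. Table 7.7:2 gives 71% power at the earlier Cmax values (gCV 32%, ratio 112%) and 68% at the earlier AUC values (54%, 104%), with no allowance for drop-outs. With power that near 70%, a term that costs almost nothing is worth having.

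**Working it through.** **Inputs from protocol section 7.7.** N=160, taken as 80 per arm; acceptance range 80-125%; Cmax gCV 32% with ratio 112%; AUC0-∞ gCV 54% with ratio 104%. The two-sided 90% CI is from section 7.3.1.

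**Inputs that are assumptions.** R, the ratio of geometric mean exposure between the two sites at equal weight (1.0 to 1.3), and p, one site's share of subjects (0.5, with 0.7 as a check). Arms are taken as balanced within site.

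**The plan's own figures.** With σ² = ln(1+gCV²), the precision is exp[t(0.95; 158) · σ · √(2/80) · √(χ²(0.95; 158)/158)]. This gives 1.093 with limits 102.44-122.45 for gCV 32% and 1.155 with limits 90.01-120.17 for gCV 54%, as in Table 7.7:1. Exact power for 80-125% is 71.6% and 68.8%, against 71% and 68% in Table 7.7:2.

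**Effect of omitting site.**
- Site variance: v = p(1−p)(ln R)².
- Planning gCV read as total variation: residual with site = σ² − v.
- Excess width on the log scale, as a share of the width without site: 1 − √[(σ² − v)/σ²].
- Coverage without site: 2·F[t(0.95; 157) · √(σ²/(σ² − v))] − 1, with F the t distribution on 157 df.
- Power: integrated over the estimated variance, on 156 df with site and 157 df without. Without site the residual sum of squares is noncentral, with noncentrality 160·v/(σ² − v).

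Example, Cmax at R=1.2 and p=0.5: σ² = ln(1+0.32²) = 0.0975; v = 0.25 × (ln 1.2)² = 0.0083; residual with site 0.0892; excess = 1 − √(0.0892/0.0975) = 4.4%.

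Equal sites, gCV as total variation:

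| | R=1.0 | 1.1 | 1.2 | 1.3 |
|---|---|---|---|---|
| Cmax: excess width (%) | 0 | 1.2 | 4.4 | 9.2 |
| Cmax: coverage without site (%) | 90.0 | 90.4 | 91.4 | 93.0 |
| Cmax: power with site (%) | 71.6 | 72.4 | 74.9 | 78.7 |
| Cmax: power without site (%) | 71.6 | 71.8 | 72.4 | 73.4 |
| AUC: excess width (%) | 0 | 0.4 | 1.6 | 3.4 |
| AUC: coverage without site (%) | 90.0 | 90.1 | 90.5 | 91.1 |
| AUC: power with site (%) | 68.8 | 69.3 | 70.6 | 72.5 |
| AUC: power without site (%) | 68.8 | 69.0 | 69.4 | 70.1 |

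**Unequal sites.** With a 70/30 split the excess width falls to 0 / 1.0 / 3.6 / 7.7% (Cmax) and 0 / 0.4 / 1.4 / 2.9% (AUC).

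**Planning gCV read as within-site.** Power with site then stays at 71.6% (Cmax) and 68.8% (AUC). Without site it is 71.6 / 70.9 / 69.1 / 66.6% and 68.8 / 68.5 / 67.6 / 66.3%.

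**Simulation check.** For Cmax, with 8000 trials per value of R, blocks of 4 within site and weight stratum, and assumed strata of 20/60/20%, the mean excess width was 0 / 1.2 / 4.4 / 9.3%. Power was 71.4 / 72.8 / 74.8 / 78.2% with site and 71.5 / 72.2 / 72.3 / 72.7% without.

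**Cost of the term.** Residual df falls from 157 to 156, and t(0.95) rises from 1.65462 to 1.65468, about 0.004%.

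**The case against.** The omission is disclosed, reasoned and the same in both documents, and the model without site is valid. The ratio analysis is exploratory, and the visible text attaches no formal decision rule to 80-125%. A slightly conservative interval therefore changes no pre-specified conclusion.

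The size rests wholly on an assumed R. Only a difference at equal weight counts, since weight is already in the model. The design also limits such differences: one product source and dose, trained staff injecting supine subjects in the thigh to supplied instructions, and a bioanalytical laboratory blinded to allocation. At R=1.1 the expected upper 90% limit moves by about 0.1 percentage point: 121.53 to 121.42 for Cmax and 118.72 to 118.65 for AUC. The power statement in section 7.7 is conditional on less variability than in the earlier trials, so comparing it with unreduced gCVs is somewhat harsh. Parts of the PK analysis text are blacked out, so a supplementary analysis with site cannot be ruled out.

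All of this stands, and it keeps the point small. It does not show that the sites have equal exposure. They are separate units with their own staff giving the injections, and protocol section 3.2 regards injection reliability as the variable most likely to matter. A hidden supplementary analysis would not alter the stated exclusion from the primary model. None of it is a reason to prefer the model without site, since the term costs practically nothing when the sites are alike.

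**Conclusion.** The concern holds as a conditional loss of precision. If the sites differ in exposure at equal weight, the planned 90% CIs are wider than they need be. The error is conservative, and the plan is internally consistent on this point. The consequence ranges from none (equal sites) through about 1% of CI width or less and under 1 point of power (site ratio 1.1) to 9.2% of width and about 5 points of power for Cmax (78.7% against 73.4% at a ratio of 1.3). AUC gains less because its residual variance is larger. These figures depend on the assumed site ratio and split, and on whether the planning gCVs already contain site variation; the documents settle none of these. The change is worth making because it can only help materially or cost almost nothing.

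**What to change.** Add site (two levels, fixed effect) to the model in protocol section 7.1 and to the covariate list in SAP section 7.1, alongside treatment and continuous baseline weight. Keep the model without site as a sensitivity analysis.

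Statistically this costs one term and one degree of freedom, and needs no new data. Administratively, a protocol amendment goes through the review described in protocol section 8.1; SAP section 3.3 is already the place where departures from the protocol analysis are recorded. Specify the term before results are seen, so that it cannot be read as data-driven.

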7.2 NULL AND ALTERNATIVE HYPOTHESES

The relative bioavailability of BI 695501 using autoinjector (A) compared to BI 695501 using prefilled syringe (B) will be estimated, in an exploratory manner, by the ratios of the geometric means (A/B) for the primary endpoints using the ANOVA described in [Section 7.1](#). All PK further parameters of interest will be analysed descriptively.

7.3 PLANNED ANALYSES

Primarily, all endpoints will be presented descriptively. The PK parameters (see [Section 5.1.1](#)) will be calculated according to the BI SOP ‘Standards and processes for analyses performed within Clinical Pharmacokinetics/ Pharmacodynamics’ ([001-MCS-36-472](#)).

The logarithmic transformed primary PK endpoints will be evaluated using scatterplots and boxplots for prefilled syringe versus autoinjector administration of BI 695501, by baseline body weight and overall.

7.3.1 Primary endpoint analyses

In an exploratory manner, the relative bioavailability of BI 695501 using autoinjector (A) compared to BI 695501 using prefilled syringe (B) will be estimated by the ratios of the geometric means (A/B) for the primary PK endpoints. Point estimates of relative bioavailability, the ratios (A/B) of the geometric means for the primary PK endpoints (see [Section 5.1.1](#)), and their two-sided 90% CIs will be provided for the overall comparison A versus B.

The PK endpoints will be log-transformed (natural logarithm) prior to fitting the ANOVA model (see [Section 7.1](#)). For each PK endpoint, the difference between the means for $\log(A)$ - $\log(B)$ will be estimated by the difference in the corresponding adjusted means (least-squares means), and a two-sided 90% CI based on the t-distribution will be computed. These quantities will then be back-transformed to the original scale to provide the point estimate and 90% CIs for the corresponding ratio of geometric means (A/B) for each PK endpoint.

The ANOVA will be conducted on the PK Analysis Set (PKS). The PKS will consist of all randomized subjects who receive the single dose of trial medication (BI 695501 using autoinjector or BI 695501 using prefilled syringe), and have at least one evaluable primary PK parameter, and are without important protocol deviations or violations thought to significantly affect the PK of BI 695501.

Pharmacokinetic parameters of a subject will be included in the analysis unless the subject has an important protocol violation relevant for the evaluation. Whether a protocol violation is important will be decided no later than in the Report Planning Meeting.

Reasons for exclusion of single pharmacokinetic parameters can for example be:

- Time deviations
- Use of restricted medications
- Dosing errors

It will also be decided in the Report Planning Meeting which subjects are to be included in the PKS.

Details of the presentation and analysis of PK data will be provided in the Trial Statistical Analysis Plan (TSAP).

7.3.4 Analysis of Safety endpoints

Safety will be assessed for the secondary and further endpoints listed in [Section 5.1.2](#) and [Section 5.1.3](#) using the Safety Analysis Set. All treated subjects (that is, all subjects who received one dose of trial drug), will be included in the Safety Analysis Set. Safety analyses will be descriptive in nature.

The safety summaries will be presented by treatment according to treatment received.

Tabulations of frequencies/proportions will be used for the evaluation of categorical (qualitative) data, and tabulations of descriptive statistics will be used to analyse continuous (quantitative) data.

Adverse events will be coded using the Medical Dictionary for Regulatory Activities (MedDRA). All events with an onset after the first dose of trial medication up to a period of 10 weeks after the last dose of the trial medication (i.e., end of the REP) will be assigned to the treatment phase for evaluation, and will be referred to as treatment emergent adverse events (TEAEs). Frequency, intensity and causal relationship of AEs will be tabulated by treatment, primary system organ class and preferred term. SAEs and other significant AEs (according to ICH E3), and protocol-specified AESIs will be listed separately (see [Section 5.3.7.1](#)).

The number and percentage of subjects with injection site reactions (assessed at Day 1 from the time of the injection until Day 2, prior to discharge from the trial site) will be summarized by treatment for each injection site reaction.

Laboratory values taken after the first dose of trial medication up to a period of 10 weeks after the last dose of the trial medication will be assigned to the treatment phase for evaluation. Descriptive statistics of laboratory values over time and for the change from baseline will be provided for each treatment group. Laboratory parameters will be compared to their reference ranges and frequency tables will be provided for the number of subjects within and outside the reference range.

Observed values and changes from baseline in BP (systolic and diastolic), PR, and body temperature will be summarized by treatment group.

Boehringer Ingelheim
BI Trial No.: 1297.13
c11534380-01

Trial Protocol

23 Aug 2016
Page 47 of 58

Proprietary confidential information © 2016 Boehringer Ingelheim International GmbH or one or more of its affiliated companies

Details of the presentation and analysis of safety data will be provided in the TSAP.

7.3.5 Pharmacokinetic and pharmacodynamic analyses

The PK parameters listed in [Section 5.1.1](#) and [Section 5.1.3](#) for drug BI 695501 will be calculated according to the relevant SOP of the Sponsor ([001-MCS-36-472](#)).

Subjects who are not included in the PKS (refer to [Section 7.3.1](#)) will be reported with their individual plasma concentrations and individual PK parameters; however, they will not be included in descriptive statistics for plasma concentrations, PK parameters or other statistical assessment.

Only concentration values within the validated concentration range and actual sampling times will be used for the calculation of PK parameters. Concentrations used in the PK calculations will be in the same format provided in the bioanalytical report (that is, to the same number of decimal places provided in the bioanalytical report).

If a pre-dose concentration value is greater than 5% of C_{max}, the subject's PK data will not be included in any statistical evaluations, in accordance with international guidance. The individual PK parameters of such a subject will be calculated and listed separately. If a pre-dose concentration is above below the limit of quantification (BLQ), but less than or equal to 5% of the subject's C_{max} value, the subject's data without any adjustments will be included in all PK measurements and calculations.

7.4 INTERIM ANALYSES

No interim analysis is planned in this study.

7.5 HANDLING OF MISSING DATA

7.5.1 Safety

With respect to AE analysis, missing relationship will be imputed to "yes". For other safety evaluation, no imputation of missing data is planned.

7.5.2 Plasma drug concentration - time profiles

Handling of missing PK data will be performed according to the relevant Corporate Procedure of the Sponsor ([001-MCS-36-472](#)).

Drug concentration data identified with NOS (no sample available), NOR (no valid result), NOA (not analysed), BLQ, or NOP (no peak detectable) will be displayed as such and not replaced by zero at any time point except the lag phase.

